7.4. Phamacokinetic Analysis Set (PKAS)

PKAS: consists of all subjects who take at least one dose of study treatment and have at least one blood sample providing evaluable concentration data.

7.5. Dose-determining Set (DDS)

DDS: consists of all subjects who have received at least 80% of the total planned dose of GFH018, are considered to have sufficient safety evaluation during the 31-day-observation period or developed DLT during the first cycle.

7.6. Protocol Deviation

Protocol deviations will be defined on a Data Review Meeting prior to the final database lock.

8. STATISTICAL METHOD

8.1. General Statistical Consideration

The statistical analysis plan be finalized prior to data base lock. All analyses and data presentations will be generated using SAS® Version 9.4 or higher software

Descriptive summary

Continuous variables: Descriptive statistics will include the number of non-missing values (n), arithmetic mean, standard deviation (SD), median, minimum and maximum values.

The minimum and maximum values will be displayed to the same decimal precision as the source data, the arithmetic mean and median values will be displayed to one more decimal than the source data, and the SD value will be displayed to two more decimals than the source data for the specific variable.

Categorical variables: Descriptive statistics will include counts and percentages per category. The denominator in all percentage calculations will be the number of participants in the relevant analysis set, unless otherwise specified. Percentages will be displayed to one decimal place with the following exceptions: 1) percentages will not be displayed for zero frequencies; 2) percentages will be displayed as "100%" when percentage is 100%.

ORR and DCR will be calculated, the corresponding two-sided 90% confidence intervals will be estimated by the Clopper-Pearson method.

Baseline

Baseline is defined as the last non-missing measurement collected on or before first study drug administration. For ECGs, the average of the ECG parameters should be used.

Censor rule

Table 3 below shows the censor rule for PFS:

Table 3 Censor rule for PFS

No.	Situation	Event or Censor / Analyais date
1	PD or death	Event / PD date or death date
2	Have at least one post-baseline assessment, no PD, no Death	Censor / Last imaging date
3	No post-baseline assessment and no Death	Censo r/ First dosing date

Only subjects with the BOR of CR or PR will be included for DOR analysis. DOR will apply the same consor rule as PFS.

Best overall response (BOR) is the best measured response at any time post treatment. Subject without any post-treatment assessments will be treated as non-responder.

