4.2. Efficacy Variables

The clinical efficacy will be evaluated by investigator per RECIST (Response Evaluation Criteria in Solid Tumors) 1.1. The efficacy variables including:

- Best overall response (BOR) is defined as the best overall response recorded from the start of treatment until disease progression or the last tumor assessment, whichever occurs earlier.
- Overall response rate (ORR) is defined as the proportion of subjects with BOR of complete response (CR) or partial response (PR).
- Disease control rate (DCR) is defined as the proportion of subjects with a BOR of CR, PR, or stable disease (SD).
- Duration of response (DOR) is defined as the time from first evidence of CR or PR to disease progression or death from any cause, whichever occurs first.

- Progression free survival (PFS) is defined as the time from start of study treatment until disease progression or death from any cause, whichever occurs first.
- Time to progression (TTP) is defined as the time from start of study treatment until disease progression.

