6. SAMPLE SIZE

Dose escalation part:

Subjects will be enrolled and treated in cohort of size 3-6. Approximately 20-40 subjects are planned to be enrolled. Additional subjects may be enrolled if more dose levels or alternative dosing regimens are to be explored.

Dose expansion part:

6-12 subjects are planned to be enrolled in each treatment. A minimum of 12 subjects should be included in the cohort of RP2D (subjects who have received the same treatment regimen will be counted).

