8.5. Efficacy Analysis

Efficacy analyses will be performed for subjects in the FAS based on RECIST evaluation.

A waterfall plot will be presented for the best percentage change from baseline in the sum of target lesion diameters. Swim plots will be prepared for all subjects to present subject drug exposure and efficacy evaluations at each visit.

The best overall response (BOR) will be determined and statistically analyzed based on evaluations at all visit, and the number and percentage of subjects with BOR of CR, PR, SD, PD, NE, and Non-CR/Non-PD will be summarized. Participants with BOR of unknown or none (i.e. no valid record of post-baseline tumor assessments) will be considered non-responsive. ORR (CR or PR) and DCR (CR, PR or SD) will be calculated based on BOR, respectively, and the Clopper-pearson method will be used to estimate ORR and DCR and their 2-sided 90% confidence intervals.

Time to progression (TTP), duration of response (DOR), and progression-free survival (PFS) will be analyzed using the Kaplan-Meier method, with their median and 90% confidence interval will be provided. If the number of subjects in a group is less than 10, only DOR, TTP and PFS listings will be provided for each subject.

Assessments of target lesion, non-target lesion, new lesion, and overall response will be listed in detail for each subject and each visit.

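### The SAP gives two conflicting windows for best overall response, one ending at progression and one open-ended, and does not say which drives ORR, DCR and entry to the DOR analysis

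*SAP*

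**What the plan says.** Three places in the SAP bear on how BOR is derived.

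- **Section 4.2 (Efficacy Variables)** defines BOR as the "best overall response recorded from the start of treatment until disease progression or the last tumor assessment, whichever occurs earlier". ORR and DCR are defined immediately afterwards as proportions based on BOR.
- **Section 8.1 (General Statistical Consideration, under the censoring rule)** defines it a second time: "Best overall response (BOR) is the best measured response at any time post treatment". No stop at progression is given.
- **Section 8.5 (Efficacy Analysis)** says that BOR will be "determined and statistically analyzed based on evaluations at all visit". This names the data used but sets no window. ORR and DCR are then calculated from BOR without saying which definition is meant.

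BOR also controls who is analysed for DOR. Section 8.1 states: "Only subjects with the BOR of CR or PR will be included for DOR analysis". It applies the PFS censoring rule to DOR, and that rule (Table 3) dates the event at progression or death. Section 4.2 measures DOR as the "time from first evidence of CR or PR to disease progression or death from any cause, whichever occurs first".

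**The concern.** Both sentences are complete definitions of one term, and neither refers to the other. Two programmers could each follow the SAP faithfully and classify the same subject differently: as a non-responder under Section 4.2 and as a responder under Section 8.1.

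Three reported results depend on the choice: ORR, DCR and the set of subjects with a DOR. PFS and TTP do not use BOR and are unaffected. The discrepancy runs in one direction, because the Section 8.1 window contains the Section 4.2 window and so can only add responders. If the choice is left until the data have been seen, it could be influenced by which definition gives the higher rate.

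**Working it through.** The SAP states no figure on this point, so there is nothing to reproduce. The check compares the texts and then illustrates the size.

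**1. When the definitions differ.** Let W1 be the Section 4.2 window (start of treatment to first progression or final assessment) and W2 the Section 8.1 window (no cut-off). W1 lies inside W2, so the best response in W2 is at least as good as that in W1. It is strictly better only if a better category is recorded after first progression. Hence:

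- ORR under W2 is at least ORR under W1. It is higher if a subject has CR or PR only after first progression.
- DCR under W2 is higher only if that subject also had no SD, PR or CR before progression. A subject with SD, then progression, then PR already counts in DCR under W1.

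**2. What happens to DOR.** Take a subject with first progression at date A and first PR at a later date B.

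- Under W1 the subject is not a responder and has no DOR.
- Under W2 the subject has a BOR of PR and must enter the DOR analysis. The clock starts at B. If first progression is the event, as Table 3 would date it for PFS, the duration is A minus B, which is negative.
- To avoid this, a later progression, death or censoring date would have to replace A. The SAP does not say so.

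**3. Size of a single reclassification.** Inputs: Section 6 says "6-12 subjects are planned to be enrolled in each treatment", with at least 12 subjects at the RP2D. Sections 8.1 and 8.5 specify two-sided 90% Clopper-Pearson intervals. Assumption: one subject whose only response follows first progression, and no other responders.

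With x responders out of n, the lower limit is the 0.05 quantile of Beta(x, n − x + 1), and the upper limit is the 0.95 quantile of Beta(x + 1, n − x). For x = 0 the lower limit is 0 and the upper limit is 1 − 0.05^(1/n). For x = 1 the lower limit is 1 − 0.95^(1/n).

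| n | ORR, Section 4.2 | 90% CI | ORR, Section 8.1 | 90% CI | Shift (1/n) |
|---|---|---|---|---|---|
| 6 | 0/6 = 0% | 0 to 39.3% | 1/6 = 16.7% | 0.9 to 58.2% | 16.7 points |
| 12 | 0/12 = 0% | 0 to 22.1% | 1/12 = 8.3% | 0.4 to 33.9% | 8.3 points |

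**The case against.** The strongest reply is that Section 8.1 is loose shorthand rather than a rival definition. Section 4.2 is where endpoints are defined, and ORR and DCR stand next to its wording. The Section 8.1 sentence leads into a rule for subjects without assessments, which Section 8.5 repeats in terms of post-baseline assessments. That suggests its reference to time after treatment means only after baseline. This is a plausible account of what was intended. It does not settle the matter: an unrestricted window is the opposite of one that ends at progression, the sentence stands in the methods section beside the rule for DOR entry, and Section 8.5 adds no cut-off either.

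A second reply is that the effect depends on tumour assessment continuing after progression, which the SAP does not address and the protocol may. This stands as a limit on size: if assessment always stops at progression, the two definitions give identical results.

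A third reply is that an interval from response to progression naturally means progression after response, so the negative duration is contrived. It is true that a reader could use a later event, but neither the DOR definition nor Table 3 says what to do when progression has already occurred. Section 8.5 also limits groups of fewer than 10 subjects to listings for DOR, TTP and PFS. In those groups the problem would appear as an impossible or arbitrary listed value rather than in a Kaplan-Meier estimate.

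Finally, efficacy is a secondary objective, no hypothesis is tested, the paired intervals overlap widely, and the planned listings and swim plots would let a reader see a late response. All of this is correct and limits the severity. It does not remove the contradiction.

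**Conclusion.** The concern holds. The SAP defines BOR in two incompatible ways and does not say which applies to ORR, DCR and DOR entry. Section 8.1 as written would count a response recorded after progression and could admit a subject to the DOR analysis with no valid duration.

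Each subject whose only response follows first progression moves ORR by 8.3 points in a cohort of 12 and by 16.7 points in a cohort of 6. Where there are no other responders, the report also changes from no responses to one. These figures illustrate a single assumed case. The SAP gives no frequency for it, and the number may be nil. Because the endpoints are secondary and descriptive, this is a point to fix rather than one that puts the trial's main conclusions at risk.

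**What to change.** - **Section 8.1:** delete the BOR sentence, or replace it with a reference to the Section 4.2 definition. Keep the separate rule that subjects without assessments count as non-responders.
- **Section 8.5:** state that BOR is derived from evaluations within the Section 4.2 window, up to and including first progression, and that ORR, DCR and DOR entry use this BOR.
- **Later assessments:** show them only in the by-visit listings and swim plots that Section 8.5 already plans.

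DOR entry then follows the same window, so no subject can enter with progression before the first response. The cost is SAP wording in two places, with no change to data collection or sample size. If any response is recorded only after progression, ORR, and possibly DCR, will be lower than under the Section 8.1 wording, by the amounts shown above; otherwise no result changes. The change should be made before database lock.

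### The SAP gives best overall response two different end points and sets no confirmation or minimum-SD rule, so a post-progression or single unconfirmed reading can raise ORR or DCR

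*SAP*

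**What the plan says.** The rule for best overall response (BOR) appears in three places.

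- Section 4.2 defines BOR as the "best overall response recorded from the start of treatment until disease progression or the last tumor assessment, whichever occurs earlier".
- Section 8.1, below the censoring table, says: "Best overall response (BOR) is the best measured response at any time post treatment".
- Section 8.5 says BOR will be "determined and statistically analyzed based on evaluations at all visit".

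The efficacy summaries follow from BOR. Section 8.5: "ORR (CR or PR) and DCR (CR, PR or SD) will be calculated based on BOR". Section 8.1: "Only subjects with the BOR of CR or PR will be included for DOR analysis". Section 4.2 starts DOR at the first evidence of CR or PR and ends it at progression or death.

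On who reads the scans, section 4.2 says: "The clinical efficacy will be evaluated by investigator per RECIST (Response Evaluation Criteria in Solid Tumors) 1.1". The SAP does not say whether CR or PR must be confirmed, or how long SD must last to count.

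**The concern.** There are two problems, of different firmness.

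The first is a contradiction. Section 4.2 stops looking for the best response at progression; section 8.1 does not stop. Two programmers, each following one section, could give the same subject different BORs and so produce different ORR and DCR tables.

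The second is that the rule is permissive under every version. The best of several readings is taken, one reading is enough, and the reader is the investigator in an open-label, non-randomized trial (section 3). A PR that is gone at the next scan counts as a response and enters DOR. An SD read once counts as disease control however early it was read. Without a confirmed figure alongside, a reader of the ORR table cannot tell lasting responses from single readings.

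Preliminary efficacy is a secondary objective (section 2). Section 3 names it among the inputs to the RDE decision and to the choice of Part II tumor types. In groups this small, the difference between no response and one response is much of what the table has to say.

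**Working it through.** **Step 1. The three rules applied to the same subject.** These are illustrative sequences of visit responses, not trial data.

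| Sequence | Section 4.2 | Section 8.1 | With confirmation and an SD time condition |
|---|---|---|---|
| SD, PD, PR | SD | PR | SD (if the SD was late enough) |
| PD, SD | PD | SD | PD |
| SD, PR, SD | PR | PR | SD (PR not confirmed) |
| very early SD, PD | SD | SD | PD |

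Rows 1 and 2 show the contradiction: ORR changes in row 1 and DCR in row 2, depending on which section is followed. Section 8.5 fits either reading because it states no stop. Rows 3 and 4 show the permissiveness: 4.2 and 8.1 agree, and both count the single reading.

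Row 1 also upsets DOR. Section 8.1 admits the subject because BOR is PR, but under section 4.2 DOR runs from first response to progression. Here progression comes before the response, so the duration is negative unless a later progression is used, and the SAP does not provide for that.

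**Step 2. Direction.** A confirmation rule, a minimum-SD rule or a stop at progression can only remove subjects from the numerators. ORR and DCR under the section 8.1 wording are therefore equal to or higher than under the stricter rules, never lower.

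**Step 3. Size per subject.** Inputs: 6 to 12 subjects per expansion treatment and at least 12 at the RP2D (section 6); two-sided 90% Clopper-Pearson intervals (sections 8.1 and 8.5). The SAP states no target ORR or power, so there is no figure of its own to reproduce.

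One reclassified subject moves a rate by 1/n: 1/6 = 16.7 points, 1/12 = 8.3 points.

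For x of n, the limits are the 5% quantile of Beta(x, n − x + 1) and the 95% quantile of Beta(x + 1, n − x). For x = 0 the lower limit is 0 and the upper is 1 − 0.05^(1/n): 22.1% for n = 12 and 39.3% for n = 6.

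| Count | Rate | 90% CI |
|---|---|---|
| 0/6 | 0% | 0 to 39.3% |
| 1/6 | 16.7% | 0.9 to 58.2% |
| 0/12 | 0% | 0 to 22.1% |
| 1/12 | 8.3% | 0.4 to 33.9% |
| 2/12 | 16.7% | 3.0 to 43.8% |
| 5/12 | 41.7% | 18.1 to 68.5% |
| 6/12 | 50.0% | 24.5 to 75.5% |

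The last two rows illustrate DCR with and without one early SD.

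**Step 4. How often it might happen.** The SAP gives no rate of unconfirmed PR. With an assumed per-subject rate q, the chance of at least one in a group is 1 − (1 − q)^n.

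| Assumed q | n = 6 | n = 12 |
|---|---|---|
| 2% | 11.4% | 21.5% |
| 5% | 26.5% | 46.0% |
| 10% | 46.9% | 71.8% |

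These show only how the chance depends on q. They do not estimate the bias in this trial.

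**The case against.** The strongest reply is that confirmation, SD duration and the scan schedule commonly sit in the protocol or in the response criteria. The SAP is based on protocol version 1.6 and names RECIST 1.1, so silence here is not an error. That would settle the matter if the SAP were silent. It instead writes its own operational rule, and a protocol rule requiring confirmation would itself conflict with taking the best reading at any time. The disagreement between 4.2 and 8.1 stands whatever the protocol says.

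Several further points are fair and limit the finding.

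- A reader might infer that the trial's ORR and DCR will be overstated. The SAP does not support that: it gives no rate of unconfirmed response and does not say whether scans continue after progression. Overstatement is possible, not shown.
- A reader might also infer that the dose or tumor-type decisions will be distorted. Efficacy is one of several inputs to the RDE, tumor types also rest on mechanism of action, and nothing says the committee works from the SAP's derived BOR tables. No hypothesis is tested (section 5) and no response threshold is set, so no error rate changes.
- For groups under 10, section 8.5 lists DOR without estimating it, so short or invalid durations affect a Kaplan-Meier estimate only in groups of 10 or more.
- Section 8.5 plans swim plots and visit-level response listings, where a transient PR would be visible. This helps a careful reader but does not change what the ORR and DCR tables count.
- The intervals before and after one reclassification overlap heavily.
- A confirmatory scan read by the same investigator does not remove reader optimism.

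**Conclusion.** The point holds in a limited form. The firm defect is the contradiction over when the BOR window closes: section 4.2 at progression or last assessment, section 8.1 at no stated point. The second defect is that no version of the rule requires confirmation of CR or PR, or a minimum time for SD. A single investigator-read PR, or an SD read at any time, therefore counts.

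The effect is 16.7 points per affected subject at n = 6 and 8.3 points at n = 12, always upward. This assumes the SAP wording is programmed as written. The total excess cannot be computed from the SAP. The matter is worth correcting before database lock because the estimates are small-sample, uncontrolled and easily misread. It does not undermine the safety objectives or any formal test.

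**What to change.** 1. Use one BOR definition, worded identically in sections 4.2, 8.1 and 8.5, that ends at progression or the last tumor assessment if earlier.
2. Report confirmed ORR (CR or PR still met at a later assessment, at the interval the protocol sets) with its 90% Clopper-Pearson interval beside unconfirmed ORR, each clearly labelled. Which is the lead figure is the sponsor's choice.
3. Count SD in DCR only if documented at or after the first scheduled post-baseline assessment, or at the protocol's minimum if it sets one. State which category an earlier SD falls into; section 8.5 already lists NE. An SD at the first scheduled scan followed by progression at the second would still count, so this guards only against very early readings.
4. Show DOR for confirmed responders, and flag unconfirmed ones in the listing and swim plot.

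The cost is revised wording plus one extra derivation and table from assessments already planned. Reported rates may be slightly less favourable.

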8.2. Subjects in Study

8.2.1. Subjects Dispostion

From screening to study completion, the following summaries will be provided:

- Summary of the number of patients who screen success for entry into the study and screen failure, respectively, and the number of subjects treated with at least 1 dose of GFH018 (All enrolled population)
- Summary of the number and percentage of treatment withdraws by primary reason and overall (full analysis set) and the number and percentage of study discontinuation by primary reason and overall (full analysis set).

A by-subject listing of reasons for screen failure reason(s), treatment discontinuation, study discontinuation with date and reasons for discontinuation.

8.2.2. Protocol Deviation

Deviations will be defined on a Data Review Meeting shortly prior to the final database lock. The major protocol deviation will be summarized in the number and percentage of subjects with a major protocol deviation by type of deviation based on the FAS.

Additionally, major protocol deviations will be provided in a data listing.

8.2.3. Demographics and Baseline Characteristics

The following demographics and baseline characters will be summarized based on FAS:

Age (years) at baseline

- Sex
- Race
- Height (cm)
- Weight (kg) at baseline
- BMI (kg/m2) at baseline
- ECOG Performance Status
- Smoking history
- Alcohol history

The following baseline characters of Tumor Diagnosis will be summarized:

- Disease diagnosis
- Primary site of cancer
- Time from initial diagnosis to start of study treatment
- TMN stage at screening
- Disease stage
- Any metastatic sites

8.2.4. Medical History/Current Medical Conditions

Medical history and current medical conditions will be coded by using the Medical Dictionary for Regulatory Activities (MedDRA) version 25.0. Medical history is the medical condition ended before the first dose date of study drug and the current medical condition is the medical condition ended on or after the first dose date of study drug. For the FAS, medical history and current medical conditions will be summarized descriptively by System Organ Class (SOC) and Preferred Term (PT). The corresponding data listing will also be provided.

8.2.5. Prior Anti-Tumor Therapy

Prior anti-tumor drug therapies will be coded using World Health Organization Drug Dictionary (WHO DD) version 202203 B3.

Based on the FAS, prior anti-tumor therapies will be summarized, and prior anti-cancer drug therapies will be summarized by Anatomical Therapeutic Chemical (ATC) Grade 4 and Preferred Term (PT).

Based on the FAS, a detailed listing of prior anti-tumor therapies will be provided.

